## INTRODUCTION

This is a multicentre, multinational study in which it is anticipated to include 110 adult subjects with acquired thrombotic thrombocytopenic purpura (TTP) from approximately 50 participating sites across approximately 13 countries in Europe, Middle East and Northern America. This population includes symptomatic patients with acute episodes of acquired TTP, requiring treatment with plasma exchange (PE). In a limited number of sites, the trial allows inclusion of adolescent subjects (age 12 - < 18 years) as per EMA PIP (EMEA-001160-PIP01-11).

TTP is a rare and life-threatening disorder of the blood coagulation system, in which accumulation of Ultra large von Willebrand factor (ULvWF) multimers has been implicated, leading to an increased risk of thrombus formation in small blood vessels due to excessive platelet aggregation and is associated with profound thrombocytopenia and erythrocyte fragmentation. The condition is characterized by systemic platelet aggregation in the microcirculation, producing fluctuating ischaemia in many organs. If sustained, this may cause tissue infarction.

ALX-0081 is a bivalent Nanobody, consisting of two identical monovalent building blocks, that target von Willebrand factor (vWF). ALX-0081 is able to interact with vWF in both its active (i.e. functional for interaction with GPIb-IX-V as regular size multimers and as ultra-large multimers) and in its inactive stage (regular size multimers prior to conformational change of A1 domain).

Given the established role of the interaction between vWF and platelet GPIb-IX-V in the pathogenesis of TTP, it is anticipated that ALX-0081 may provide a new option for the treatment of this condition. Therefore, targeting the activity of ULvWF and preventing the interaction with GPIb-IX-V is an attractive concept for treatment and prevention of thrombotic complications in TTP.

The research conducted into TTP over the past three decades has improved the understanding of the pathophysiology of the disease allowing for the potential development of novel agents targeting the underlying disease processes. There are no currently approved therapies for TTP,

---

and although there are newer therapies currently undergoing evaluation, the studies of these potential treatments are at a relatively early stage.

ALX-0081 represents a novel approach to the treatment of TTP and the information available from in vitro, in vivo and early clinical studies all suggest a clear rationale for its use in this disease and a reasonable expectation that it will provide significant benefit in terms of efficacy, safety and quality of life for subjects with TTP. Through its inhibition of ULvWF-mediated platelet aggregation and resulting antithrombotic effect ALX-0081 may permit more rapid control of acute episodes of TTP when used in combination with PE. This would potentially reduce the risk of organ ischaemia and a more rapid normalization of the platelet count could also reduce the risk of haemorrhagic complications. Its use may also result in improved outcomes in poorly responsive subjects, including those with secondary TTP where mortality from the disease remains high. In addition, ALX-0081 may be of value in the prevention of relapses after recovery from an acute episode.

### 1.1 Study Objectives

The objectives of this study are as follows:

#### *Primary*

- Reduction of time-to-response, defined by the achievement of laboratory blood marker response (platelets), confirmed at 48 hours after the initial reporting of this response (platelets and LDH).

#### *Secondary (including longer-term disease sequelae)*

- Improvement in number of subjects responding to therapy
- Reduction in PE procedure-related items
- Reduction of time to resolution or improvement of signs and symptoms typical of TTP, including blood markers
- Reduction of number of exacerbations (defined as recurrent thrombocytopenia following a response and requiring a re-initiation of daily PE treatment after  $\geq 1$  day but  $\leq 30$  days after the last daily PE) and relapses (defined as de novo event of TTP that occurs later than 30 days after the last daily PE)

- 
- Improvement of cognitive level at steady state post acute phase (adults only)
  - Improvement of clinical symptoms and organ function
  - Reduction in mortality within the PE treatment period and within the subsequent study drug treatment period (including tapering)
  - Reduction of concomitant treatment-related complications
  - Evaluation of safety and immunogenicity of adjunctive treatment with ALX-0081
  - Determination of pharmacokinetic (PK) and pharmacodynamic (PD) characteristics of ALX-0081 in subjects with acquired TTP

## 1.2 Study Design

This is a Phase II multicentre, single-blinded, parallel design, randomised, placebo-controlled study. After confirmation of eligibility to study participation, adult subjects will be randomised in a ratio of 1:1 to either receive ALX-0081 or placebo as adjunctive therapy to PE. Adolescent subjects will not be randomised and will be treated with ALX-0081.

Adult subjects will receive a first intravenous (i.v.) bolus of 10 mg ALX-0081 or placebo via push injection within 6h, but not later than 15 minutes prior to the initiation of PE on study (which can either be the very first PE session, if the subject was randomised prior to the initiation of PE, or the second PE session, if the subject was randomised after one, single PE session). This first PE on study is followed by subcutaneous (s.c.) administration of 10 mg study drug. Adolescent subjects will receive weight-based doses according to the same administration schedule as adults.

Subsequently daily s.c. administrations of 10 mg ALX-0081 or placebo will follow each PE session for the duration of PE (including tapering and PE given for exacerbations) and once daily for 30 days following the last PE. The maximum total daily dose of study drug is 10 mg when administered in conjunction with PE (20 mg only in case twice daily PE sessions are needed) and 10 mg when in period following last PE. Study drug administration will continue in case of re-initiation of PE for an exacerbation of TTP with a maximum total treatment duration limited to 90 days after first administration of study drug. At 30 days after the last day of study drug administration, subjects will be assessed for the primary and secondary endpoints of the study and will be followed for a maximum of 1 year for relapses and other tertiary (longer-term) endpoints.

Laboratory parameters for inclusion, study conduct, safety assessments and assessments of response/relapse, re-treatment and study medication dose modification will be assessed at each local site laboratory.

[figure not shown]
### 1.3 Study Timepoints

The subjects will be followed in 3 different phases during this study:

- Screening ( $\leq 12$  hours prior to first PE on study and study drug) and baseline (15 minutes-6 hours prior to first PE on study and study drug)
- Treatment Phase:
  - Daily PE adjunctive s.c. treatment phase
  - Day 1 after the last daily PE
  - Post daily PE s.c. treatment phase (including PE tapering)
- Follow-up Phase (after completion of study drug treatment):
  - Day 3 (+/- 1 day)
  - Day 7 (+/- 1 day)
  - Month 1 (+/- 3 days)
  - Month 2 (+/- 7 days)
  - Month 3 (+/- 15 days)
  - Month 6 (+/- 15 days)
  - Month 12 (+/- 15 days)

Subjects enrolled into the study under earlier versions of the protocol will also be followed up at Days 1, 2, 4, 5 and 6 of the Follow-Up Phase. Data for these time points will be included in summary tables and listings only for those subjects where the data was collected. Due to the lack of meaningful interpretation of a percentage based on the number of subjects in the population, the percentage for these time points will not be presented.

[Figure 1](#) displays a schematic overview of the different study phases and [Appendix I](#) contains the general schedule of assessments for this study.

**Figure 1: Schematic overview of pre-treatment, treatment and follow-up phases.**

\* Subjects will be randomised prior to the start of PE treatment. In exceptional cases however (due to need or ability to start PE in a time frame which does not allow all required screening and/or baseline study procedures to be performed), a subject may be randomised after the first, single PE session, but prior to the start of the second PE session. This overall second PE session should be started within 24 hours of the very first PE, and will be considered the first PE on study.

## 2. STUDY POPULATIONS

Four subject populations will provide the basis for all statistical analyses, data evaluations and summaries of the adult subjects.

Safety Population: The safety population includes all subjects who received at least one dose or partial dose of study drug, with treatment assignment designated according to actual treatment received.

Actual treatment received is not collected in the study database. [REDACTED] [REDACTED] will record the details of any subject receiving treatment that does not correspond to their randomised treatment assignment. Actual treatment received will be defined as being equal to randomised treatment assignment for a particular subject unless the incorrect treatment was administered for the majority of the subject's time on treatment.

Intent-to-Treat (ITT) Population: The intent-to-treat population includes all randomised subjects, according to the randomised treatment assignment. The ITT population will be the primary population of interest for efficacy analyses.

Per-Protocol (PP) Population: The per-protocol population includes all randomised subjects, according to the randomised treatment assignments who have no major protocol deviations (see [Appendix II](#)) and satisfactorily complete the study. The PP population will be a subset of the ITT population and will be the secondary population of interest for efficacy analyses.

Subjects to be excluded from the PP Population will be defined prior to the database lock according to criteria as per [Appendix II](#) without regard to study drug assignment. [Appendix II](#) describes the major protocol deviations affecting the statistical analysis of the study and their derivation; an extensive tracker of all clinical protocol deviations is maintained separately by [REDACTED].

---

Pharmacokinetic (PK) Population: The PK population will consist of all subjects who received the study drug and for whom the primary PK data are considered to be sufficient and interpretable. The PK analysis will utilize the PK population.

Adolescent subject data will be described separately from the adult subjects. There will be no formal statistical analysis of adolescent data, only listings. Data for adolescent subjects will be grouped separately from adult subject data within the listings.

---

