10.1 Study Populations

Populations for the primary and secondary endpoint analyses

The primary analysis population will be the intent-to-treat (ITT) population, which will consist of all randomised subjects according to the randomised treatment assignment. In addition, for the efficacy analyses, the per protocol population (PP) will be used. The PP population will be a subset of the ITT population and will consist of all randomised subjects, according to the randomised treatment assignment, with exclusion of all major protocol violators.

Population for the safety analysis

The safety population will consist of all subjects who received at least one dose of study drug, with treatment assignment designated according to actual treatment received.

Population for the PK analyses

The PK analyses will be performed on the PK population, which will consist of all subjects who have received study drug and for whom the primary PK data are considered to be sufficient and interpretable.

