## 6.4 Safety Analysis

Analysis of all safety data will be performed on the safety analysis population.

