#### **6.4.6 Bleeding Events**

Clinically relevant bleeding is the main potential risk based on the pharmacological action of ALX-0081. Clinically relevant bleeding is assessed daily during daily PE period, on the first day after the daily PE period and then weekly for the subsequent time interval until 30 days after the last PE session and during any unscheduled visits. The number of subjects who experience clinically relevant bleeding and the number of subjects requiring surgical and/or medical intervention will be tabulated by treatment group and summarised by visit using counts and percentages.

Bleeding according to the modified ITP bleeding score is assessed daily during daily PE period, on the first day after the daily PE period and then weekly for the subsequent time interval until 30 days after the last PE session and during any unscheduled visits. Modified ITP bleeding score will be summarised for each parameter by treatment group and visit using counts and percentages. The sum of the parameter scores for each subject at each time point will be summarised using descriptive statistics for continuous variables.

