One or more incorrect (i.e. not as per randomised treatment assignment) treatment administrations		██████████	Review of CTMS entries Review of listings	Incorrect treatment administered (placebo/verum instead of verum/placebo)	Treatment non compliance
Administered more than protocol prescribed dose (overdose): if more than 1 dose and no or 1 PE on that day if more than 2 doses and not 2 PEs on that day		██████████	Review of CTMS entries	Subject overdosed (x doses instead of y)	Treatment non compliance
One PE prior to randomisation					

Major PD categories	Remarks	Source	How to assess?	DVTERM	DVDECOD
Prior to protocol amendment 12 any PE prior to randomisation is considered a major protocol deviation	Ablynx maintain a listing of which protocol version each subject is enrolled under. This will need to be used in collaboration with the PE and randomisation dates from the database in order to identify violating subjects.	██████████ ██████████	Review of listings or check	X PE done before randomisation	Eligibility criteria not met
Starting from protocol amendment 12 first PE ended more than 24h prior to randomisation is considered a major protocol deviation.	As above	██████████ ██████████	Review of listings or check	PE done x hours before randomisation	Eligibility criteria not met
Starting from protocol amendment 12 more than one PE prior to randomisation is a major protocol deviation	As above	██████████ ██████████	Review of listings or check	X PE done before randomisation	Eligibility criteria not met
Other					
Disallowed concomitant therapy taken: only one disallowed = desmopressin	Any concomitant medication with HTC code "H01BA" (coded term "VASOPRESSIN AND ANALOGUES").	██████████	Review of listings	Disallowed medication taken (name of drug, start date – stop date)	Excluded concomitant medication
Subject becomes pregnant but is not withdrawn from the trial		██████████	Review of listings	Subject pregnant but not withdrawn	Subject not withdrawn as per protocol
Subject is lost to follow up but is not withdrawn from the trial	If a subject is lost to follow up, they should be in the database as discontinued otherwise a query should fire, so at the end of the study there should be no subjects lost to follow-up who were not withdrawn.			Subject lost to follow up but not withdrawn	Subject not withdrawn as per protocol

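### The SAP's majority-of-time rule for actual treatment can place bleeds that occurred on ALX-0081 in the placebo column of the safety tables

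*SAP*

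**What the plan says.** Protocol section 10.1 defines the safety population as everyone who had at least one dose, "with treatment assignment designated according to actual treatment received". It gives no threshold and does not mention a subject who received both products.

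SAP section 2 repeats that definition and then makes it operational. It states that "Actual treatment received is not collected in the study database" and that details of any wrong-treatment subject will be recorded separately. Actual treatment is then set equal to the randomised arm "unless the incorrect treatment was administered for the majority of the" subject's treatment time.

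The rule feeds every safety output. SAP section 6.4 says "Analysis of all safety data will be performed on the safety analysis population". SAP section 6.4.6 says "Clinically relevant bleeding is the main potential risk based on the pharmacological action of ALX-0081", and the counts of subjects with such bleeding "will be tabulated by treatment group and summarised by visit using counts and percentages". Pharmacodynamic tables (SAP section 6.5.2) use the same population.

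The plan foresees wrong-product errors. SAP Appendix II makes this a major deviation: "One or more incorrect (i.e. not as per randomised treatment assignment) treatment administrations".

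**The concern.** A subject's safety column should reflect the drug that could have caused the event. Under the majority rule it reflects which product filled more of the calendar. The two can differ in exactly the case the rule was written for, a subject who received both products.

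Two routes put a bleed on active drug into the placebo column:

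- **Placebo subject, minority on ALX-0081.** The subject stays under placebo, with any bleed that occurred on ALX-0081.
- **ALX-0081 subject, majority on placebo.** The subject moves to placebo and takes along any bleed from the time on ALX-0081.

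Each lowers the observed ALX-0081 bleeding rate and raises the placebo rate. For a safety comparison of the main expected risk, that is the wrong direction in which to err.

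**Working it through.** The plan gives no figure to reproduce here. The check has three parts.

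**1. Does any other text repair the rule?**

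| Place | What it does | Repairs the rule? |
|---|---|---|
| SAP 6.4.1 | Treatment-emergent status depends on onset relative to the first dose of study drug, whichever product that was | No |
| SAP 6.4.6 | Tabulates bleeding by treatment group and visit | No |
| SAP 6.2.2 | Lets the sponsor decide on excluding subjects or parameters after a deviation | Case by case, no set rule |
| SAP Appendix II | Makes one wrong administration a major deviation | Removes the subject from the PP population only |
| Protocol 10.3 | Ties an adverse event to the treatment and time that preceded it | Would help, but is not carried into the SAP |
| SAP 6.1.5 | Lists changes from the protocol | Does not mention the majority rule |

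So one wrong dose removes a subject from the PP population, while wrong doses on up to half the course leave the safety column unchanged.

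**2. How much ALX-0081 can a placebo subject receive and stay under placebo?**

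Majority means more than 50%, so the limit is T/2 for a course of T days, rounded down to whole days.

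- T = 90 (the protocol maximum): 45 days
- T = 60: 30 days
- T = 36 (assumed: 6 days of daily PE plus 30 days after): 18 days, which covers the whole daily-PE phase
- T = 31: 15 days

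The SAP does not say whether the majority is counted in days or in doses.

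**3. What does one misplaced bleed do?**

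The planned size is 110 adults randomised 1:1, so 110/2 = 55 per arm. The documents give no expected bleeding rate, so the counts below are assumed. In each row, one placebo subject bled while on ALX-0081 for half the course or less. Under an any-dose rule both the bleed and the subject move, giving denominators 56 and 54.

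| SAP rule, ALX-0081 vs placebo | Difference | Any-dose rule | Difference | Narrowing |
|---|---|---|---|---|
| 3/55 vs 1/55 (5.5% vs 1.8%) | 3.6 | 4/56 vs 0/54 (7.1% vs 0.0%) | 7.1 | 3.5 |
| 5/55 vs 2/55 (9.1% vs 3.6%) | 5.5 | 6/56 vs 1/54 (10.7% vs 1.9%) | 8.9 | 3.4 |
| 8/55 vs 4/55 (14.5% vs 7.3%) | 7.3 | 9/56 vs 3/54 (16.1% vs 5.6%) | 10.5 | 3.2 |

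Differences and narrowing are in percentage points, computed before rounding. One such subject narrows the difference by about 3.2 to 3.5 points.

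The reverse route is similar. With assumed counts of 5/54 vs 2/56 under the SAP rule, the difference is 9.3 − 3.6 = 5.7. Returning the subject and the bleed gives 6/55 vs 1/55, a difference of 10.9 − 1.8 = 9.1, so the narrowing is 3.4 points.

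**The case against.** **The SAP defines the protocol term; it does not replace it.** A reader might infer that the SAP overrides the protocol. The documents do not support that. The SAP keeps the protocol's sentence and adds a convention for mixed exposure, on which protocol section 10.1 is silent. Any one-column rule must put such a subject somewhere. What stands against the SAP is that its convention can place active-drug bleeds under placebo and is not declared in section 6.1.5.

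**Bleeding latency is not documented.** A reader might infer that bleeding follows exposure within hours. The documents show that only for RICO: in protocol Table 6, a single 10 mg s.c. dose brought it below 20% in 3 of 3 subjects, starting at 2 to 6 hours. For bleeding, protocol Table 7 suggests that duration matters: 2 of 15 single-dose ALX-0081 subjects (0 of 3 at 10 mg) against 10 of 12 with 7 or 14 daily doses, with 2 of 4 on multiple-dose placebo. The numbers are very small. This weakens any claim that one stray dose is decisive. It does not justify counting a bleed during up to half a course of ALX-0081 as a placebo event.

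**Such subjects may not exist.** The investigator is told the allocation (protocol section 7.5) and vial numbers are logged for in-hospital and home use (section 6.5). No error rate is given. This limits the size of the point but does not repair the rule.

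**The errors are partly visible already.** Major deviations are listed and summarised by arm, and all adverse events are listed. But no output promises dates of each product or the product preceding an event.

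**An any-dose rule has costs.** It can move a mostly-placebo subject's whole event record to ALX-0081, and treatment-emergent status in the SAP has no end date. Applied to the whole safety population, it would also put mostly-placebo RICO, vWF and FVIII values in the ALX-0081 pharmacodynamic summary. That objection stands, and the fix is limited accordingly.

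**Protocol section 10.3 may be narrower than it reads.** Its sentence is explained by an example about events before dosing, so it may mainly concern timing. The two documents still need to be reconciled.

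**Conclusion.** The point holds as a defect in a stated rule, not as evidence of bias in this trial's results. By the wording of SAP section 2, a bleed on ALX-0081 during up to half the course in a placebo subject is tabulated under placebo. So is a bleed on ALX-0081 in a subject randomised to it who spent most of the time on placebo. Nothing else in the SAP corrects either case.

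The size is about 3.2 to 3.5 percentage points on the observed difference per such bleed. This rests on 55 subjects per arm and assumed counts from 3 vs 1 to 8 vs 4. A reader might take twice 1/55, or 3.6 points, as the effect. That is a ceiling which holds the denominators fixed, although the subject moves as well. The number of affected subjects is not stated and may be zero. Protocol section 10.3 excludes formal testing of safety data, so no test result depends on this. The change is worth making because it is cheap and concerns the main expected risk.

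**What to change.** 1. In SAP section 2, for adverse-event and bleeding tables only, count any subject with at least one full or partial dose of ALX-0081 under ALX-0081. Leave the pharmacodynamic summaries in section 6.5.2 on the existing rule.
2. Add a listing of every mixed-exposure subject with the dates of each product, and show for each adverse event the product last received before onset.
3. Record the rule in SAP section 6.1.5 and reconcile it with protocol section 10.3.

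The cost is a short SAP amendment and one listing. The listing needs data from outside the study database, namely the wrong-treatment records that SAP section 2 already provides for and, where necessary, the drug accountability logs. The statistical downside is that some events from placebo time will appear under ALX-0081. That is the conservative direction for safety, and the listing makes it visible.
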